1.0 Background

Recently, ultrasonography (US) has experienced a rapid evolution in the field of rheumatology, an evolution certainly driven by the broad applicability of point-of-care (POC) US for the assessment of rheumatic diseases. Despite the use of US in many other medical fields, such as gynecology, emergency or gastroenterology for much longer, the uptake by the rheumatology community was only initiated in the last two decades. This is mostly due to the fact that most of the structures that are assessed in rheumatology are very superficial, and the technology to generate a high resolution view for these superficial structures, to a degree of being able to detect even mild inflammatory changes, have been developed relatively recently.

US is made up of mechanical sound waves that can transmit through different materials like fluids, soft tissues and solids. Different tissues have different properties in terms of how much they transmit or reflect these waves and it makes them appear different on the screen. The Brightness mode (B mode) is the basic mode most commonly used and it is very helpful to determine if there is any inflammation in the investigated structure. In a much more sensitive manner than physical examination, B mode will detect structural changes associated with the presence of inflammation. In addition, it is possible to detect moving objects (such as erythrocytes) with US and convert such signal to an image, which is the principle of the Doppler view. Again, the Doppler has been used for a long time in other fields, such as cardiology, to detect the occlusion of carotid arteries, thrombosis of the deep veins or valvular insufficiencies of the heart. However, high erythrocyte velocities are characteristic of the latter pathologies and this is mostly not applicable to rheumatology practice. The neovascularisation within joints or tendons are at the capillary level and the flow is much slower. Power Doppler mode has been the recent breakthrough imaging technology in rheumatology as it allows the detection of active inflammation in a very sensitive manner.

Nowadays, rheumatologists typically use US for guided injections and for the assessment of joint structures, connective and vascular tissues, and related pathologies.¹ When it comes to the assessment of musculoskeletal (MSK) structures, the value of US lies upon a unifying principle for many arthritides: rapid detection of highly relevant and often times subclinical features of disease. For example, in a rapidly progressing disease like Rheumatoid Arthritis (RA), US allows faster detection of synovitis and bone erosion, resulting in earlier fulfillment of diagnostic criteria.²

Early disease detection with US perhaps takes its most relevant sense in psoriatic arthritis (PsA), where efforts are currently being deployed to intercept disease in its transition from psoriasis (PsO).

Three clinically quiet disease stages have recently been proposed between PsO and clinically detected PsA (see illustration 1)³ :

- A preclinical phase (aberrant activation of the immune system)
- A subclinical PsA phase (soluble biomarkers and imaging findings with no clinical symptoms)
- A prodromal PsA arthralgia and fatigue with no synovitis and or enthesitis on physical exam yet

[figure not shown]

Illustration 1. Transition phases from psoriasis to early PsA

US is the imaging technique at the core of disease characterization during the latter 2 quiet stages. In the sub-clinical phase, several studies report more enthesal inflammation and synovitis on ultrasonography in PsO patients vs. healthy controls (HC). During the prodromal phase, a clinical and sonographic study on PsO patients with arthralgia revealed that sonographically determined tenosynovitis was the most significant contributor to symptoms and that sonographically determined enthesitis was linked to the future evolution of PsA. The identification of specific imaging lesions, associated with overt clinical PsA development, will be the challenge for the coming years, in order to correctly identify PsO patients at risk for PsA development.³

The DUET (Diagnostic Ultrasound Enthesitis Tool) study, headed by our group, the GRAPPA US working group, is working towards deriving a sonographic enthesitis scoring system accurately

distinguishing early PsA from non-PsA patients (including osteoarthritis (OA) patients with PsO), over the coming year.⁴ Prior to diagnosis, there is great value attributed to PsA screening within the PsO population in the dermatology setting. As such, US was proven to be a great complement to the Early Arthritis for Psoriatic Patients (EARP) screening questionnaires and Psoriasis Epidemiology Screening Tool (PEST), increasing the specificity of referrals from 9% to 77% without compromising sensitivity.⁵

The use of US is not limited to RA and PsA in rheumatology. US detection of subclinical synovitis, seen in a large proportion of systemic lupus erythematosus (SLE) patients, could also reveal to be a great asset for early SLE patient management.⁶ Overuse tendinopathies are group of MSK pathologies without a systemic component frequently seen by rheumatologists. Shoulder pain, for example, is second to low back pain as the most frequent MSK complaint leading to referral for rheumatological assessment.⁷ Tendinopathies of the rotator cuff are diagnosed with greatest cost-efficiency, sensitivity and specificity using MSK US. The same imaging technique is also used for the guided peritendinous administration of several therapeutic agents, including corticosteroids, Hyaluronic Acid (HA) and sclerosis agents, to avoid intratendinous injections.⁸ Combining these two US applications has already shown to improve therapeutic efficiency.⁹ OA, the most common form of arthritis (affecting 25–50% of US adults by age 85) and frequent contributor to disability, is another rheumatic disease for which recent advances brought US frontstage.¹⁰ There is growing support for the utility of US in OA assessment, as it is more sensitive than conventional radiography which may allow earlier disease identification. Additionally, US provides detailed imaging of soft tissues and inflammation, allowing detection of a variety of features relevant to OA, including osteophytes, effusions, synovitis, enthesitis, bursitis, and cartilage pathology, in a more cost-effective manner than MRI.¹⁰ The OMERACT group recently released updated definitions of US-detected pathologies with pertinence in OA. The most relevant were synovitis, erosion and enthesitis.¹¹ One caveat remains in the assessment of OA enthesopathy with US: it is a feature shared with PsA, and thus creates the need for differentiation between early PsA and OA patients suffering from comorbid PsO. Concluding on the broad applicability of POC US in rheumatology, giant cell arteritis (GCA) and Sjögren Syndrome are examples of inflammatory diseases of vascular and connective tissue respectively, for which US plays a role in diagnosis. In GCA, US could contribute to reducing the risk of permanent sight loss associated with diagnostic

delay.¹² In Sjögren, US assessment of salivary glands is an important non-invasive measure supporting the diagnostic process.¹³

Moving on to the subject of ultrasonography scanners as medical devices; more specifically the high quality US scanners and high-resolution transducers required for the practice of rheumatology. A number of barriers persist and stand in the way of a wider use of POC US for the detection, diagnosis and management of rheumatic diseases. A significant one is the acquisition and maintenance costs of high quality instruments, limiting accessibility for community practitioners. There are recent technical and technological advances in the field of handheld ultrasonography that are set to overcome the access barrier. Typically, the cost of acquisition of scanners with a greyscale frequency of at least 13 MHz and a Doppler frequency of at least 8 MHz ranges from 25 000CAD to 90 000CAD. Hand-held US technology promises to take this cost down to a price tag under 10,000CAD with the introduction of affordable high-definition scanners possessing the specifications/requirements for use in the rheumatology practice (Greyscale frequency: 12 - 20 MHz and Doppler frequency: 8 - 12 MHz). Clarius Mobile Health Inc., an innovative company based out of Vancouver B.C., produces such devices. Clarius US scanner have regulatory approval by the FDA and Health Canada. However, before they can be specifically used for the practice of rheumatology, their performance needs to be validated against gold-standard devices for key interventions.

US holds significant promise as an imaging tool in rheumatology and in the future, handheld US could be used at the bedside to provide diagnostic and prognostic information, as well as guide both systemic and local treatment decisions and applications. Through the accurate assessment of disease extension and activity (e.g. presence of enthesitis in a PsA patient presenting with primarily as synovial disease), the bedside application of US in standard assessment of the PsA patients will enable the understanding of which domains are involved and would require treatment/and which treatment based on the domain involved. There are numerous advantages of the hand-held US devices over the existing gold standard devices for being accessible by more physicians, therefore by more patients. The ability to carry the device in their pocket will allow the physicians to be able to use in multiple settings, e.g. in different offices or inpatient vs outpatient clinics. Making the bedside US a part of the clinical assessment will avoid any delays in diagnosis and lead to earlier treatments. In addition, it increases the patients adherence to therapy adjustments.¹⁴ As such, the

goal of this trial will be to validate two affordable handheld MSK US scanner against gold-standard devices through an assessment of their accuracy for:

- visualizing anatomical structures and pathologies
- detecting vascular flow

2.0 Aim

Our aim to test the concurrent validity of the Clarius handheld US devices versus gold-standard device to detect characteristic features of healthy and rheumatic joints (i.e. anatomical structures and vascular flow).

3.0 Study Objectives

Primary objective:

To determine whether handheld US devices (Clarius HD3 L20 and L15 scanners) B mode are as accurate as gold standard device (GE Logic E9/S8) at visualizing intraarticular synovitis

Secondary objectives:

1. To determine whether handheld US devices (Clarius HD3 L20 and L15 scanners) power Doppler mode are as accurate as gold standard device (GE Logic E9/S8) at detecting intrasynovial signals
2. To determine whether handheld US devices (Clarius HD3 L20 and L15 scanners) B mode are as accurate as gold standard device (GE Logic E9/S8) at visualizing tenosynovitis
3. To determine whether handheld US devices (Clarius HD3 L20 and L15 scanners) power Doppler mode are as accurate as gold standard device (GE Logic E9/S8) at detecting intratendineous signals
4. To determine whether handheld US devices (Clarius HD3 L20 and L15 scanners) B mode are as accurate as gold standard device (GE Logic E9/S8) at visualizing bone erosions
5. To determine whether handheld US devices (Clarius HD3 L20 and L15 scanners) B mode are as accurate as gold standard device (GE Logic E9/S8) at grading intraarticular synovitis

6. To determine whether handheld US devices (Clarius HD3 L20 and L15 scanners) power Doppler mode are as accurate as gold standard device (GE Logic E9/S8) at grading intrasynovial signals
7. To determine whether handheld US devices (Clarius HD3 L20 and L15 scanners) B mode are as accurate as gold standard device (GE Logic E9/S8) at grading bone erosions
8. To determine whether handheld US devices (Clarius HD3 L20 and L15 scanners) power Doppler mode are as accurate as gold standard device (GE Logic E9/S8) at visualizing elementary lesions of enthesitis
9. To determine whether handheld US devices (Clarius HD3 L20 and L15 scanners) power Doppler mode are as accurate as gold standard device (GE Logic E9/S8) at detecting enthesal signals
10. To determine whether handheld US devices (Clarius HD3 L20 and L15 scanners) B-mode are as accurate as gold standard device (GE Logic E9/S8) at detecting trilaminar appearance of the nail plate abnormalities

4.0 Approaches and Methods

Number of arms: single arm (repeating an image collection protocol with hand held US and the gold standard devices for each patient)

Blinding: The scoring of the US images will be done in a blinded fashion. The de-identified images from different patients and different scanners will be pooled to ensure the principle investigators (PIs) blindness to both the patients' clinical findings and the scores of other imaging modality.

4.1 Study Population

Adult patients with peripheral PsA that is not in minimal disease activity (MDA) and presenting at least one tender and swollen joint.

Inclusion Criteria

- Age ≥ 18
- Meets the classification for psoriatic arthritis (CASPAR) criteria
- Able to provide an informed consent
- Having peripheral disease phenotype of PsA
- At least one tender and swollen joint on the day of US

Exclusion Criteria

- Having isolated axial PsA
- Being in MDA with no tender and swollen joints

4.2 Clinical Data Collection

There will only be one study visit. The consent, clinical data collection and US assessments will be done with the same study visit.

Clinical Assessment: This will be performed by an experienced rheumatologist on each site. The following information will be collected:

Patient's age, gender, Body Mass Index (BMI), physical activity, smoking, treatments and disease activity, based on 66/68 joint count for tender and swollen joints, Spondyloarthritis Research Consortium of Canada (SPARCC) enthesitis index, number of dactylitic digits, body surface area for skin disease and presence of nail disease.

For the Patient-Reported Outcomes (PROs), pain Visual Analogy Scale (VAS), patient global and Health Assessment Questionnaire Disability Index (HAQ-DI) will be collected.

Medical device incident collection and documentation: Both US machines are approved by Health Canada and FDA. If any incident occurs, this will be reported to the manufacturer and applicable Health Authorities as per medical device regulations and will also be included in the final report that will be provided to the REB.

4.3 Ultrasound Protocol (Assessment of Joints and Enthesis)

Each patient will have consecutive (same day) US examinations using the Clarius handheld and GE gold-standard devices. All scans will be performed in a darkened room. Power Doppler settings will be standardized with a pulse repetition frequency of 500 Hz and low wall filters. The colour gain will be increased to the highest value where power Doppler signals under the bony cortex are not generated. There will be no further training for this step as the 3 investigators have done multiple research projects together and separately, with reproducibility being tested and presented.¹⁵ However, there will be a investigators meeting prior to data collection to review all anatomical sites, positioning and standard views and agree on labelling. All images will be labeled to identify anatomical site and laterality. A glossary will be provided for labelling, to ensure blinding in the later stages. At least one B mode and one power Doppler image will be saved for each site and lesion. The standard will be saving the images in longitudinal views. Transverse views will be saved if there is an abnormality noted on the long axis.

Representative images will be collected and saved for all of the following structures bilaterally:

Joints (24 total): 2nd-3rd metacarpophalangeal (MCP), 2nd-3rd proximal interphalangeal (PIP), 2nd-3rd distal interphalangeal (DIP), wrist, elbow, shoulder, knee, ankle and 5th metatarsophalangeal (MTP) joints of the foot, bilaterally. For the MCP, PIP and DIP joints, if joints other than the 2nd or 3rd present with swelling (e.g. 4th or 5th) they will be scanned instead. This approach is to ensure a maximum number of swollen joints will be assessed.

Entheses (20 total):

Large entheses: Supraspinatus, triceps, common extensor tendon, quadriceps, patellar ligament (origin and insertion), Achilles tendon, Plantar fascia insertions;

Small entheses: extensor digitorum tendon insertion at the DIP and PIP level

Tendons (4 total): Extensor digitorum tendon of the second digits, tibialis posterior tendon in the ankles

Nail: In case of having a nail PsO, the most involved nail and contralateral side will be assessed. If there is no nail PsO, procedure will be performed on the nail of the 2nd digit of the hands.

All study procedures and that will take place in one study visit, as summarize in Table-1.

Table-1: Assessment schedule

Procedures	Visit 1
Obtain informed Consent	x
Inclusion/Exclusion criteria	x
Demographics	x
Relevant medical history	x
Current Psoriatic Arthritis treatment	x
Pain VAS	x
Patient global assessment	x
HAQ-DI	x
Disease activity (66/68 joint count)	x
SPARCC enthesitis index	x
Dactylitis count	x
BSA	x
Presence of nail disease	x
Ultrasound protocol using both machines	x
Documentation of the ESR and CRP (if already done as standard of care)	x
Adverse event collection	x

VAS: Visual Analogue Scale; HAQ-DI: Health Assessment Questionnaire Disability Index; SPARCC: Spondloarthritis Research Consortium of Canada; BSA: Body Surface Area; ESR: Erythrocyte Sedimentation Rate; CRP: C-reactive protein

Scanners/probes that will be used for each anatomical site is summarized in Table-2.

Table-2: Probes/scanners, views and anatomical sites

Anatomical site	Views	GE Logic E9/S8	Clarius L15	Clarius L20
2 nd MCP joints	dorsal and lateral	X	X	X
3 rd MCP joints	dorsal	X		X
2 nd -3 rd PIP, 2 nd -3 rd DIP	dorsal	X		X
Wrist	dorsal	X	X	X
5 th MTP joints	dorsal and lateral	X		X
Elbow joints	posterior	X	X	
Shoulder joints	posterior	X	X	
Knee joints	anterosuperior	X	X	
Ankle joints	anterior	X	X	
Nails	dorsal	X		X
Achilles tendon insertions	posterior	X	X	X
Supraspinatus tendon insertions	lateral	X	X	
Triceps tendon insertions	posterior	X	X	
Common extensor tendon origins	lateral	X	X	
Quadriceps tendon insertions	anterior	X	X	
Patellar ligament (origin and insertion)	anterior	X	X	

Plantar fascia insertions	plantar	X	X	
Extensor digitorum tendon insertions at DIP and PIP	dorsal	X		X
Extensor digitorum tendon of the second digits	dorsal	X		X
Tibialis posterior tendon	medial	X	X	

MCP: metacarpophalangeal; PIP: proximal interphalangeal; DIP: distal interphalangeal (DIP); MTP: metatarsophalangeal

Subject ID: Every study subject will be given unique study ID. This will consist of site ID and patient number respectively (Site IDs will be 01 for OHRI, 02 for Women College and 03 for University of Florida).

Labelling: During the ultrasound scan every image that is saved will be given a label by the local research assistant.

Exporting: After each scan, all the images of each study subject will be exported in JPEG format. The images will be saved in a file with the subject ID, which will be unique. This file will be sent to the central site (OHRI) using Sharepoint by the local research assistant.

Blinding: At the central site (OHRI), the research assistant will give a unique identifier number to each image, for a random quality control and for cross referencing whenever needed. The cropped images, as detailed below, will not have the subject ID visible to the PI at the time of reading but will be accessible for the quality control. (read-only access). The research assistant at OHRI is the only site personnel who has the capacity to uncrop the images in the PowerPoint file (password protected files).

For interim analysis, image reading will be performed after the first 10 patients. Final reading will be done after all patients are recruited. Images will be scored by the principal investigator at OHRI. Images will not contain any identifiable information such as Date of Birth (DOB) or initials. The US images will be transferred to a PowerPoint file by the research assistant at OHRI in JPEG

format. The research assistant will generate an unblinded master list, inaccessible to other site personnel, to link the slide numbers with the patients and scanned anatomical sites and the slide will have no other information on the patient number or ID. For scoring the images by the PI, a random order slide show will be conducted, irrespective of the machine used or the anatomical site or patient assessed, to ensure blindness to data related to the patient identifiers (The PI will not be blinded to the machine that the image was taken with as the JPEG format that is achieved from different machines are identifiable, but due to the random order scoring, images that belong to the same joint by the different machines are not to be scored consecutively). There will be nine separate powerpoint files, for images of joints, tendons, entheses, nail including power Doppler and gray scale findings; and grey scale file for erosions. Scoring will be done using previously validated methods as detailed below.

During the data collection, there will be interim analysis: Interim analysis will be done after 10 patients being recruited. The readings and scorings will be done by the principal investigator at OHRI center, following the exact methodology as above.

The grading of greyscale intraarticular synovitis and power Doppler intrasynovial signals will be done based on the OMERACT definitions (scales of 0-3) as follows^{16, 17} :

Greyscale inflammatory (hypoechoic) synovial hyperplasia:

- **Grade 0:** no hypoechoic synovial hyperplasia
- **Grade 1:** minimal hypoechoic synovial hyperplasia (filling the angle between the periarticular bones, without bulging over the line linking tops of the bones)
- **Grade 2:** hypoechoic synovial hyperplasia bulging over the line linking tops of the periarticular bones but without extension along the bone diaphysis
- **Grade 3:** hypoechoic synovial hyperplasia bulging over the line linking tops of the periarticular bones and with extension to at least one of the bone diaphyses

Power Doppler signal:

- **Grade 0:** no flow in the hypoechoic synovial hyperplasia
- **Grade 1:** up to three single spots signals or up to two confluent spots or one confluent spot plus up to two single spots

- **Grade 2:** vessel signals in less than half of the area of the synovium ($\leq 50\%$)
- **Grade 3:** vessel signals in more than half of the area of the synovium ($> 50\%$)

Elementary lesions of enthesitis will be defined and scored as per the GRAPPA US working group's definitions, as used in the multicenter DUET study co-supported by Novartis¹⁸ :

Hypoechoicity: Distinct loss of homogenous fibrillar pattern with relative hypoechoicity compared to the rest of the enthesis after correcting for anisotropy.

- **Grade 0:** Absent
- **Grade 1:** Present

Thickening: Increased thickness of the tendon/ligament at the enthesis compared to its body. Thickness may be difficult to judge and should be suspected when accompanied by other enthesal lesions.

- **Grade 0:** Absent
- **Grade 1:** Present

Bone Erosion: A cortical defect confirmed with a step-down contour defect detected in two planes at the insertion of the tendon/ligament to the bone.

- **Grade 0:** Absent
- **Grade 1:** Present

Enthesophyte: A step-up bony prominence at the normal bone contour. Grade the severity of the enthesophyte based on its length. Although the readers are not expected to measure the length of the enthesis we provided suggested cut off points to guide the grading of the enthesophytes

- **Grade 0 :** No enthesophytes
- **Grade 1 :** Small enthesophyte
- **Grade 2 :** Medium enthesophyte
- **Grade 3 :** Large enthesophyte

Calcification: Hyperechoic linear structures detected within the tendon/ligament at the insertion to the bone but with no congruency with the bone.

- **Grade 0 :** No calcifications
- **Grade 1 :** Punctate hyperechoic area
- **Grade 2:** Linear calcification without acoustic shadow
- **Grade 3:** Egg-shell calcification with posterior acoustic shadow

Doppler Signal: The presence of positive Doppler signal at the enthesis, confirmed in two perpendicular planes and distinguished from reflection of surface artifacts and nutritional vessel signal.

The intensity of the Doppler signal at the enthesis will be graded using a semi-quantitative score.

Note: we will consider any Doppler signal at the enthesis area including signals appearing beyond 2 mm of the bony cortex, however, not including Doppler signals at the bursa which will be scored separately.

We will score the intensity of the Doppler signal on a semi quantitative grading system:

- **Grade 0:** No Doppler signal
- **Grade 1:** A single confluent Doppler signal or up to 3 discrete Doppler spots
- **Grade 2:** Doppler signal affecting less than half of the enthesis
- **Grade 3:** Doppler signal covering more than half of the enthesis

In addition, the **location of each Doppler signal** will be recorded:

- **Zone 1:** $\leq 2\text{mm}$ from the bone cortex – Zone 1
- **Zone 2:** $>2\text{mm}$ from the bone cortex – Zone 2

4.4 Statistical Analysis:

The primary endpoint analysis will be the interrater agreement of detecting any synovitis in B mode with the Clarius and gold standard machine. The kappa coefficients will be evaluated using the guideline outlined by Landis and Koch, where the strength of the kappa coefficients are: 0.01-0.20 slight; 0.21-0.40 fair; 0.41-0.60 moderate; 0.61-0.80 substantial; 0.81-1.00 almost perfect.¹⁹

For secondary outcomes, the interrater agreement for the presence of Doppler signals within the joints, tenosynovitis, erosions, nail, as well as features of enthesitis (hypoechogenicity, thickening, erosions, enthesophytes, calcifications) will also be evaluated using the same method. The agreement of the semiquantitative grading of the intraarticular findings' severity (synovitis in B mode, Doppler signals, erosions, each being on a scale between 0-3) will be done using weighted kappa analysis.²⁰

An interim analysis will be done after 10 patients. A moderate level of interrater agreement within that sample size (primary outcome) will allow parallel initiation of subsequent studies proposed in the research framework.

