5.1.2. Secondary Outcomes

5.1.2.1. Joints

After the imaging of all patients is completed, the intraarticular Doppler scoring will be done based on the OMERACT definitions (scales of 0-3) (Table 1):^{5,6}

Power Doppler signal:

Grade 0: no flow in the hypoechoic synovial hyperplasia

Grade 1: up to three single spots signals or up to two confluent spots or one confluent spot plus up to two single spots

Grade 2: vessel signals in less than half of the area of the synovium ($\leq 50\%$)

Grade 3: vessel signals in more than half of the area of the synovium ($> 50\%$)

Also, a lateral view of the 2nd metacarpophalangeal and 5th metatarsophalangeal joints will be recorded in the baseline visit for erosion assessment. Erosions will be described as intra-articular discontinuity of the bony surface seen in 2 perpendicular planes and will be evaluated after the imaging of all patients is completed.

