- **Doppler Signal:** The presence of positive Doppler signal at the enthesis, confirmed in two perpendicular planes and distinguished from reflection of surface artifacts and nutritional vessel signal.

The intensity of the Doppler signal at the enthesis will be graded using a semi-quantitative score.

Note: We will consider any Doppler signal at the enthesis area including signals appearing beyond 2 mm of the bony cortex.

We will score the intensity of the Doppler signal on a semi quantitative grading system:

Grade 0: No Doppler signal

Grade 1: A single confluent Doppler signal or up to 3 discrete Doppler spots

Grade 2: Doppler signal affecting less than half of the enthesis

Grade 3: Doppler signal covering more than half of the enthesis

In addition, the location of each Doppler signal will be recorded:

Zone 1: ≤ 2 mm from the bone cortex

Zone 2: > 2 mm from the bone cortex

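### Transverse views are saved only where the person scanning noted an abnormality, so a bedside negative can block a positive entheseal erosion or Doppler score, and a transverse slide can cue the central reader at joints.

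*Protocol*

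**What the plan says.** Protocol 4.3 sets a minimum image set: "At least one B mode and one power Doppler image will be saved for each site and lesion". The default orientation is fixed: "The standard will be saving the images in longitudinal views". The second plane is conditional: "Transverse views will be saved if there is an abnormality noted on the long axis".

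Three outcomes are defined by two planes:
- Entheseal bone erosion (Protocol 4.3; SAP 5.1.2.4): "A cortical defect confirmed with a step-down contour defect detected in two planes at the insertion of the tendon/ligament to the bone".
- Entheseal Doppler (Protocol 4.3; SAP 5.1.2.4): "The presence of positive Doppler signal at the enthesis, confirmed in two perpendicular planes".
- Joint erosion (SAP 5.1.2.1): "Erosions will be described as intra-articular discontinuity of the bony surface seen in 2 perpendicular planes".

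For joint erosion the SAP plans a further view that does not depend on what is seen: "a lateral view of the 2nd metacarpophalangeal and 5th metatarsophalangeal joints will be recorded in the baseline visit for erosion assessment". Table 2 of the protocol agrees, listing dorsal and lateral views for those two joints. For each enthesis, Table 2 lists one approach and no second plane.

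One central reader scores stored images in random order (Protocol 4.3; SAP 2.2). Protocol 4.0 wants that reader blind to the patient's clinical findings and to the other modality's scores. The primary outcome, any B-mode synovitis, has no two-plane condition (SAP 5.1.1 and 5.2).

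**The concern.** The comparison is meant to rest on masked central scoring of comparable images from each device. The rule for transverse views lets a bedside judgement into that scoring in two ways. First, where an outcome needs two planes, a site without a saved transverse view cannot be scored positive, so the negative was in effect given during scanning. Secondly, the mere presence of a transverse slide tells the reader that somebody noted an abnormality.

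No masking of the person scanning is described. That person must know which device is in hand, and because swelling decides which finger joints are scanned, probably knows the clinical findings too. That the person scanning is unmasked is therefore an inference, but a well-supported one. If one impression drives saving on both devices, the agreement reported between devices partly reflects that impression and not the images.

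**Working it through.** **1. The plan's own figure.** SAP 2.3 gives 683 joints for kappa 0.61, prevalence 20% and a 95% interval of full width 0.15. With n = 4z²V/w² and V = (1−κ)[(1−κ)(1−2κ) + κ(2−κ)/(2p(1−p))]:
- V = 0.39 × [0.39 × (−0.22) + 0.61 × 1.39/0.32] = 0.9999
- n = 4 × 1.96² × 0.9999/0.15² = 682.9, so 683.

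The figure reproduces, with joints treated as independent. Nothing below alters it. At 24 joints per patient it leads to 30 patients (720 joints).

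**2. Which outcomes the rule reaches.**

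| Outcome | Two planes needed | Second view saved whatever is seen |
|---|---|---|
| Entheseal erosion | yes | no |
| Entheseal Doppler | yes | no |
| Joint erosion, 2nd MCP and 5th MTP | yes | lateral view, yes; not stated whether dorsal plus lateral counts as perpendicular |
| B-mode synovitis (primary) | no | not applicable |

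The first two rows are clearly affected: 20 entheses × 30 patients = 600 sites. The third covers 4 joints × 30 = 120 sites and is unclear, not clearly affected.

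**3. What happens to a site without a transverse view.** SAP 5.3 drops a site from all probes if an image is missing on any of them. It does not say whether a transverse view that was never triggered is missing or negative. Suppose one device triggers it and the other does not. Read as missing, the site is deleted, and with it a likely disagreement. Read as negative, the untriggered device is fixed at negative without a second plane having been available to read.

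**4. Illustration of the effect on kappa.** The documents give no inputs for this, so all of these are assumed: true prevalence 5–20%; reader sensitivity/specificity 0.75/0.92 or 0.80/0.95 per device, with reader errors independent between devices; sensitivity/specificity of the saving decision 0.7/0.9, 0.8/0.95 or 0.9/0.9; an unsaved view scores negative. That makes 18 scenarios. With equal marginals, κ = (P11 − p²)/[p(1−p)], where p is the positive rate on each device and P11 the rate positive on both.

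Worked case: prevalence 20%, reader 0.80/0.95, saving 0.8/0.95.
- Both planes always saved: p = 0.2×0.80 + 0.8×0.05 = 0.200; P11 = 0.2×0.64 + 0.8×0.0025 = 0.130; κ = 0.090/0.160 = 0.56.
- One impression governs both devices: p = 0.2×0.8×0.80 + 0.8×0.05×0.05 = 0.130; P11 = 0.2×0.8×0.64 + 0.8×0.05×0.0025 = 0.1025; κ = 0.0856/0.1131 = 0.76.
- Separate decision per device: p = 0.130; P11 = 0.2×0.64² + 0.8×0.0025² = 0.0819; κ = 0.0650/0.1131 = 0.57.
- Saved on both if either device triggers: saving probabilities become 0.96 and 0.0975; p = 0.1575; P11 = 0.1231; κ = 0.0983/0.1327 = 0.74.

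Ranges over the 18 scenarios:
- always saved: 0.21–0.56
- one shared impression: 0.59–0.76
- separate decisions: 0.39–0.65
- either-device trigger: 0.53–0.74, above always-saved in all 18.

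A shared decision raised kappa every time. Separate decisions moved it either way, more so once an assumed reader cue was added (half of negative calls turned positive when a transverse view exists: 0.20–0.56).

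**5. Reach into the primary outcome.** Two routes exist, both only at joints where a transverse view was saved. One is the cue. The other is unequal material: neither document limits the joint deck to longitudinal views or says how several images of one joint become one grade, so a device with an extra image has an extra chance of a positive.

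**The case against.** The strongest reply is that this is ordinary sequential confirmation. Every site has a B-mode and a power Doppler image, longitudinal by default. A lesion truly absent on the long axis cannot meet a two-plane definition anyway. The bedside judgement matters only where the reader would see on the long-axis image something that was not flagged during scanning. It can block a positive but not create one, since the reader still scores whatever is saved. A lesion visible on one device only may also be the very device difference under study. Finally, slides are shown in random order without patient ID, so a transverse slide is not easily tied to the longitudinal slide of the same joint.

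Most of this stands and limits the point. It does not remove it: blocking positives is enough to change agreement, random order does not hide that a slide is transverse, and a genuine device difference should emerge from comparable images and not from which images were kept.

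A reader might infer more in two places. The first is that the bedside decides every two-plane outcome. The unconditional lateral view at the 2nd MCP and 5th MTP contradicts that. The second is that all 720 primary-outcome joints are at risk, with 25 readings separating failure from success. The arithmetic is right, since 720 × (0.61 − 0.50) × 0.32 = 25.3, but it is only the distance between two kappas. It does not estimate bias, and the cue reaches only joints with a saved transverse view.

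**Conclusion.** The concern holds in a limited form. For entheseal erosion and entheseal Doppler, the saving rule lets a bedside negative block a positive central score at any of 600 entheses, and the SAP does not say how such a site is scored. For joints, the rule works against the blinding aim and can give the devices unequal image sets; the primary outcome is exposed only through these two routes. Whether joint erosion is affected depends on whether dorsal plus lateral meets the perpendicular-plane definition, which the documents leave open.

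The size and direction of the bias cannot be derived, because the documents do not say who scans, in what order, or whether one person uses both devices. The modelled kappas rest on assumed inputs. They show that the 0.61 threshold could be crossed with no change in device performance, not that it will be. The point is worth correcting because the repair is cheap.

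**What to change.** In Protocol 4.3, with matching text in SAP 5.1 and 5.3:

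1. **Primary deck.** Build the B-mode synovitis deck only from the pre-set longitudinal views of Table 2, using the same views for each device compared at a joint. Keep triggered transverse images out of it.
2. **Joint erosion sites.** At the 2nd MCP and 5th MTP, save both perpendicular planes on every assigned device whatever is seen. Cost: at most 2 × 3 probes + 2 × 2 probes = 10 extra B-mode frames per patient, fewer if the lateral view is declared to be the second plane.
3. **Entheseal erosion and Doppler.** Choose one of two options. (a) Save the second plane on every assigned device whatever is seen. Table 2 gives per side Achilles 3, supraspinatus 2, triceps 2, common extensor 2, quadriceps 2, patellar origin and insertion 4, plantar fascia 2, and extensor at DIP and PIP 4. That is 21 per side and 42 site-probe combinations per patient, each in B mode and Doppler (at most 84 frames). (b) Score both outcomes from the long-axis image alone and describe them as single-plane. This adds no frames but departs from the stated definitions. Under either option, report by device the number of sites without a second plane.

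Do not adopt the cheaper-looking rule that a view triggered on one device is then saved on all. It leaves unflagged sites without a second plane, and a shared trigger can inflate kappa (step 4 of the working).

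The downside is more frames and some scanning time. No extra staff or visits are needed, and the sample size stays as it is.
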